2.0 OBJECTIVES**2.1 Primary objective**

To test the comparative effectiveness of decision aids (DA's) on patient knowledge.

2.2 Secondary objectives

- 2.2.1** To test the impact of in-visit DA's alone compared to usual care on quality of life outcomes and treatment utilization.
- 2.2.2** To test the impact of out-of-visit DA's alone compared to usual care on quality of life outcomes and treatment utilization.
- 2.2.3** To test the impact of combined in-visit and out-of-visit DA's compared to both usual care and individual DAs on quality of life outcomes and treatment utilization.
- 2.2.4** To test the comparative effectiveness of DA's on minority men's knowledge.
- 2.2.5** To compare clinic time required to administer the DA's across arms.

3.0 PATIENT SELECTION

For questions regarding eligibility criteria, see the Study Resources page. Please note that the Study Chair cannot grant waivers to eligibility requirements.

3.1 On-Study Guidelines

This clinical trial can fulfill its objectives only if patients appropriate for this trial are enrolled. All relevant medical and other considerations should be taken into account when deciding whether this protocol is appropriate for a particular patient.

Although they will not be considered formal eligibility (exclusion) criteria, physicians should recognize that the following may seriously increase the risk to the patient entering this protocol:

- Psychiatric illness which would prevent the patient from giving informed consent.

3.2 Eligibility Criteria

- **3.2.1 Documentation of disease:** Patients must have prostate biopsy within 4 months prior to registration showing newly diagnosed prostate cancer, stage T₁₋₃N₀ or xM₀ or x. In addition, patients must have:
 - Gleason score 6-10
- **3.2.2 PSA < 50 ng/mL**
- **3.2.3 Patients who have had a history of non-cutaneous malignancy in the previous 5 years are not eligible.** Exception: Patients with history of non-melanoma skin cancer are eligible.
- **3.2.4 Scheduled prostate cancer consultation to be the first consultation after diagnosis** (i.e. not a second-opinion or a consultation following previous discussions of treatment options).
- **3.2.5 Patients may not be concurrently enrolled to another clinical trial for the treatment of cancer.** Co-enrollment to biospecimen studies is allowed. Patients may be enrolled to other clinical trials after completing all of the baseline interventions and measures.
- **3.2.6 Patients with impaired decision-making capacity (such as with a diagnosis of dementia or memory loss) are not eligible for this study.** Since the primary outcome of the study is knowledge, including patients determined to have impaired decision-making capacity may confound analysis.

3.2.7 Patients must be able to read and comprehend English. Non-English-speaking patients may participate so long as an interpreter (e.g., family member, clinic staff, etc.) is present for consent, for the Decision Aid administration, and gathering of baseline and follow-up measures.

3.2.8 Age \geq 18 years

4.0 PATIENT REGISTRATION

4.1 CTEP/DCP Registration Procedures

Food and Drug Administration (FDA) regulations and National Cancer Institute (NCI) policy require all individuals contributing to NCI-sponsored trials to register and to renew their registration annually. To register, all individuals must obtain a Cancer Therapy Evaluation Program (CTEP) Identity and Access Management (IAM) account [REDACTED]. In addition, persons with a registration type of Investigator (IVR), Non-Physician Investigator (NPIVR), or Associate Plus (AP) (i.e., clinical site staff requiring write access to OPEN, Rave, or TRIAD or acting as a primary site contact) must complete their annual registration using CTEP's web-based Registration and Credential Repository (RCR) [REDACTED]. Documentation requirements per registration type are outlined in the table below.

Documentation Required	IVR	NPIVR	AP	A
FDA Form 1572	✓	✓		
Financial Disclosure Form	✓	✓	✓	
NCI Biosketch (education, training, employment, license, and certification)	✓	✓	✓	
HSP/GCP training	✓	✓	✓	
Agent Shipment Form (if applicable)	✓			
CV (optional)	✓	✓	✓	

An active CTEP-IAM user account and appropriate RCR registration is required to access all CTEP and CTSU (Cancer Trials Support Unit) websites and applications. In addition, IVRs and NPIVRs must list all clinical practice sites and IRBs covering their practice sites on the FDA Form 1572 in RCR to allow the following:

- Added to a site roster
- Assigned the treating, credit, consenting, or drug shipment (IVR only) tasks in OPEN
- Act as the site-protocol PI on the IRB approval

Additional information can be found on the CTEP website at [REDACTED] For questions, please contact the RCR Help Desk by email at [REDACTED]

4.2 CTSU Registration Procedures

This study is supported by the NCI Cancer Trials Support Unit (CTSU).

IRB Approval:

Each investigator or group of investigators at a clinical site must obtain IRB approval for this protocol and submit IRB approval and supporting documentation to the CTSU Regulatory Office before they can be approved to enroll patients. Assignment of site registration status in the CTSU Regulatory Support System (RSS) uses extensive data to make a determination of whether a site has fulfilled all regulatory criteria including but not limited to the following:

- An active Federal Wide Assurance (FWA) number
- An active roster affiliation with the Lead Network or a participating organization
- A valid IRB approval
- Compliance with all protocol specific requirements.

In addition, the site-protocol Principal Investigator (PI) must meet the following criteria:

- Active registration status
- The IRB number of the site IRB of record listed on their Form FDA 1572
- An active status on a participating roster at the registering site.

Sites participating on the NCI CIRB initiative that are approved by the CIRB for this study are not required to submit IRB approval documentation to the CTSU Regulatory Office. For sites using the CIRB, IRB approval information is received from the CIRB and applied to the RSS in an automated process. Signatory Institutions must submit a Study Specific Worksheet for Local Context (SSW) to the CIRB via IRB Manager to indicate their intent to open the study locally. The CIRB's approval of the SSW is then communicated to the CTSU Regulatory Office. In order for the SSW approval to be processed, the Signatory Institution must inform the CTSU which CIRB-approved institutions aligned with the Signatory Institution are participating in the study.

4.2.1 Downloading Site Registration Documents

Site registration forms may be downloaded from the A191402CD protocol page located on the CTSU members' website. Permission to view and download this protocol and its supporting documents is restricted and is based on person and site roster assignment housed in the CTSU RSS.

- Go to [REDACTED] and log in to the members' area using your CTEP-IAM username and password
- Click on the Protocols tab in the upper left of your screen
- Either enter the protocol # in the search field at the top of the protocol tree, or
- Click on the By Lead Organization folder to expand
- Click on the Alliance link to expand, then select trial protocol #A191402CD
- Click on LPO Documents, select the Site Registration documents link, and download and complete the forms provided.

4.2.2 Requirements for A191402CD Site Registration

- IRB approval (For sites not participating via the NCI CIRB; local IRB documentation, an IRB-signed CTSU IRB Certification Form, Protocol of Human Subjects Assurance Identification/IRB Certification/Declaration of Exemption Form, or combination is accepted).

4.2.3 Submitting Regulatory Requirements

Submit required forms and documents to the CTSU Regulatory Office via the Regulatory Submission Portal, where they will be entered and tracked in the CTSU RSS.

Regulatory Submission Portal: [REDACTED] → Regulatory Tab →
Regulatory Submission Portal

When applicable, original documents should be mailed to:
[REDACTED]
[REDACTED]

Institutions with patients waiting that are unable to use the Portal should alert the CTSU Regulatory Office immediately at [REDACTED] in order to receive further instruction and support.

4.2.4 Checking Your Site's Registration Status

You can verify your site registration status on the members' section of the CTSU website.

- Go to [REDACTED] and log in to the members' area using your CTEP-IAM username and password
- Click on the Regulatory tab
- Click on the Site Registration tab
- Enter your 5-character CTEP Institution Code and click on Go

Note: The status given only reflects compliance with IRB documentation and institutional compliance with protocol-specific requirements outlined by the Lead Network. It does not reflect compliance with protocol requirements for individuals participating on the protocol or the enrolling investigator's status with the NCI or their affiliated networks.

4.2.5 Limited access information

Institutions that are interested in participating in this study must first contact the Study Chair, [name] [REDACTED] to review study requirements and procedures and to identify who will be responsible for the study at their respective institution. See Section 13.1.

4.3 Patient Registration Requirements

- **Informed consent:** the patient must be aware of the neoplastic nature of his/her disease and willingly consent after being informed of the procedure to be followed, the experimental nature of the interventions being tested, alternatives, potential benefits, side-effects, risks, and discomforts. Current human subjects protection committee approval of this protocol and a consent form is required prior to patient consent and registration.
- **Patient completed booklets:** Patient questionnaire booklets are to be ordered prior to the registration of any patients. Patient completed booklets can be ordered by downloading and completing the booklet order form (located under the supplemental documents section of the A191402CD website) and faxing the form to Attn: Operational Support Clerk at [REDACTED]. Samples of the booklets are found in Appendices I and II, which are to be used for reference and IRB submission only. They are not to be used for patient completion.

- **Institutional randomization:** Institutions will be randomized to one of four intervention arms:
 - 1) During- and pre-consultation decision aids
 - 2) Pre-consultation decision aid only
 - 3) During-consultation decision aid only
 - 4) Usual care

The Alliance Statistics and Data Center will randomize institutions once an institution is interested and eligible to participate. All men enrolled at a site will receive the intervention to which the treating institution is randomized.

Specifically, the lead study statistician will randomly assign the initial participating institutions to one of the arms before the study is activated. The randomization will be stratified by center type (i.e. which minority group, if any, the center is “targeting”); so that if for example, there were four initial centers which specialized in Native American/Native Alaskan men, each would be assigned to one of the four arms by randomly selecting one of the four repeatedly without replacement, each time assigning that center to one of the remaining arms. This will be done separately for all center types. For all of these centers, the lead statistician will obtain CTEP Institutional IDs (as well as IDs for affiliates, if any, that may be participating), and will then provide the Alliance randomization center with the initial set of CTEP IDs for each treatment arm.

Thus, when a patient enrolls at one of the initial participating institutions, the CTEP ID of the center can be checked against the initial randomization list, which will determine which treatment that patient gets (and all patients at that center). In addition, the lead statistician will create a random sequence of arm assignments for additional institutions of each type that join after the study begins, so that whenever a new center joins the study, an arm will already have been determined for that center.

4.4 Patient Registration/Randomization Procedures

Patient enrollment will be facilitated using the Oncology Patient Enrollment Network (OPEN). OPEN is a web-based registration system available on a 24/7 basis. To access OPEN, the site user must have an active CTEP-IAM account (check at [REDACTED]) and a 'Registrar' role on either the LPO or participating organization roster. Registrars must hold a minimum of an AP registration type.

All site staff will use OPEN to enroll patients to this study. It is integrated with the CTSU Enterprise System for regulatory and roster data and, upon enrollment, initializes the patient in the Rave database. OPEN can be accessed at [REDACTED] or from the OPEN tab on the CTSU members' side of the website at [REDACTED]. To assign an IVR or NPIVR as the treating, crediting, consenting, drug shipment (IVR only), or investigator receiving a transfer in OPEN, the IVR or NPIVR must list on their Form FDA 1572 in RCR the IRB number used on the site's IRB approval.

Prior to accessing OPEN, site staff should verify the following:

[figure not shown]
- All eligibility criteria have been met within the protocol stated timeframes.
- All patients have signed an appropriate consent form and HIPAA authorization form (if applicable).

Note: The OPEN system will provide the site with a printable confirmation of registration and treatment information. Please print this confirmation for your records.

Further instructional information is provided on the OPEN tab of the CTSU members' side of the CTSU website at [REDACTED]. For any additional questions contact the CTSU Help Desk at [REDACTED]

4.5 Stratification and Treatment Assignments

While not formal stratification factors, randomization will be set up so that sites will the particular capacities to oversample minority populations will be distributed between the arms, as illustrated in the diagram below.

Grouping Factors/Treatment assignments:

- Arm 1: Pre -and During Consultation Decision Aids
- Arm 2: Pre-Consultation Decision Aid only
- Arm 3: During Consultation Decision Aid only
- Arm 4: Usual Care

5.0**STUDY CALENDAR**

Laboratory and clinical parameters during treatment are to be followed using individual institutional guidelines and the best clinical judgment of the responsible physician. It is expected that patients on this study will be cared for by physicians experienced in the treatment and supportive care of patients on this trial.

Pre-Study Testing Intervals

- To be completed \leq 28 DAYS before registration: History and physical.
- To be completed \leq 90 DAYS before registration: PSA
- To be completed \leq 4 MONTHS before registration: Prostate Biopsy

	Prior to Registration	Baseline*	12 months after baseline**
Test and Observations			
History and Physical	X		
Height	X		
Weight	X		
Prostate biopsy	X		
Chart Review			X(1)
Labs and Staging			
PSA	X		
QOL Instruments			
Baseline Questionnaire		X(2)	
One-year Questionnaire			X(3)

* To be administered following the surgical consultation

** +/- 6 weeks

- 1 At 12 months site staff will review the patient's chart from the 6-month point to the 12-month time-point, collecting treatment information and any pertinent events.
- 2 Includes the Prostate Cancer Treatment Questionnaire and the Decisional Conflict Scale. See Section 10.0 and Appendix I.
- 3 Includes Expanded Prostate Cancer Index Composite (EPIC-26) and the Decisional Regret Scale. See Section 10.0 and Appendix II. To be completed by the patient during a clinic visit. If no clinic visit is scheduled +/- 6 weeks from the 12-month time-point, study staff should mail the 12-month questionnaire with a self-addressed stamped envelope to the patient for him to complete at home and return by mail (see Section 8.3.1).

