6.0 DATA AND SPECIMEN SUBMISSION

6.1 Data Collection and Submission

Data collection for this study will be done exclusively through the Medidata Rave clinical data management system. Access to the trial in Rave is granted through the iMedidata application to all persons with the appropriate roles assigned in Regulatory Support System (RSS). To access Rave via iMedidata, the site user must have an active CTEP-IAM account (check at [REDACTED] and the appropriate Rave role (Rave CRA, Read-Only, Site Investigator) on either the LPO or participating organization roster at the enrolling site.

Upon initial site registration approval for the study in RSS, all persons with Rave roles assigned on the appropriate roster will be sent a study invitation e-mail from iMedidata. To accept the invitation, site users must log into the Select Login [REDACTED] using their CTEP-IAM user name and password, and click on the “accept” link in the upper right-corner of the iMedidata page. Please note, site users will not be able to access the study in Rave until all required Medidata and study specific trainings are completed. Trainings will be in the form of electronic learnings (eLearnings), and can be accessed by clicking on the link in the upper right pane of the iMedidata screen.

Users who have not previously activated their iMedidata/Rave account at the time of initial site registration approval for the study in RSS will also receive a separate invitation from iMedidata to activate their account. Account activation instructions are located on the CTSU website, Rave tab under the Rave resource materials (Medidata Account Activation and Study Invitation Acceptance). Additional information on iMedidata/Rave is available on the CTSU members’ website under the Rave tab at [REDACTED] or by contacting the CTSU Help Desk at [REDACTED] or by e-mail at [REDACTED]

A Schedule of Forms is available on the Alliance study webpage, within the Case Report Forms section.

Patient-completed questionnaire booklets for this study are to be ordered prior to the registration of any patients (see Section 4.4). Samples of questionnaire booklets are available in Appendices I and II for reference and IRB submission only. They are not to be used for patient completion. Booklets must be given to patients to complete and patients should be instructed to return the booklets to site staff either in person or by mail and site staff will enter patient and caregiver responses into Rave.

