8.2.5 Baseline Questionnaire

After consultation with the physician, the study coordinator will escort the patient to a private area preferably near to the patient waiting area, and provide the Baseline Questionnaire for the patient to complete before leaving.

8.3 12-month follow up

Follow up to ascertain the patient's overall and disease specific quality of life and prostate cancer treatment regret will be conducted by site coordinators 12 months (+/- 6 weeks) after the patient's consultation.

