8.3.2 Twelve-month follow-up chart review

At this time site staff will also conduct retrospective chart review to ascertain treatment utilization and complete the follow-up form. Treatment utilization will be categorized by the type of treatment the patient had (surgery vs. radiation vs. active surveillance).

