11.0 END OF INTERVENTION

11.1 Duration of Treatment

The study intervention will take place in one day and follow-up assessments will occur at 12 months following the intervention.

11.2 Managing ineligible patients and registered patients who never receive protocol intervention

Definition of ineligible patients

A study participant who is registered to the trial but does not meet all of the eligibility criteria is deemed to be ineligible.

Follow-up for ineligible patients who continue with protocol intervention

Patients who are deemed ineligible after registering may continue the protocol intervention, provided the treating physician, study chair, and executive officer agree there are no safety concerns if the patient continues protocol intervention. All tests and data submission are to continue as if the patient were eligible. Notification of the local IRB may be necessary per local IRB policies.

Follow-up for ineligible patients who discontinue protocol intervention

For patients who are deemed ineligible after registering to the trial, who start the study intervention, but then discontinue the intervention, the same data submission requirements are to be followed as for those patients who are eligible and who discontinue study participation.

Follow-up for patients who are registered, but who never start study intervention

For all study participants who are registered to the trial but who never receive study intervention (regardless of eligibility), baseline and off-treatment notice data submission required. See the Data Submission Schedule accompanying the All Forms Packet.

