12.4 Supplementary Analysis Plans

12.4.1 Secondary endpoints

Secondary endpoints will be decisional quality, as measured by the DCS and Decisional Regret; clinical time required; patient QOL, which will be measured by questionnaires and converted into continuous summary scores using standard algorithms; and utilization, which will be categorized by the type of treatment the patient received, as determined by chart review at 12 months post-diagnosis. We will also consider the primary outcome of knowledge within only minority men (pooled) (defined as non-White or Hispanic White), as well as separately within the three racial subgroups. It is worth noting that some patients may receive a follow-up biopsy before these secondary endpoints are measured (at 12 months after first consultation), which could have a strong impact on their DCS and QOL scores. Thus, whether or not a patient receives a follow-up biopsy before 12 months (and the timing of this biopsy) will be taken into account when modeling these endpoints.

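### Study calendar footnote 1 starts the only follow-up chart review at month 6, but Section 12.4.1 needs follow-up biopsies from before 12 months and, by implication, all treatment received since the consultation

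*Combined protocol and SAP*

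**What the plan says.** The study calendar in Section 5.0 has three columns: before registration, baseline, and 12 months after baseline. Chart Review is marked only in the last. Footnote 1 defines it: site staff look at the "chart from the 6-month point to the 12-month time-point, collecting treatment information and any pertinent events". The prostate biopsy row is marked only before registration.

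Section 8.3 dates the follow-up, which "will be conducted by site coordinators 12 months (+/- 6 weeks) after the patient's consultation". Section 8.3.2 adds a retrospective chart review at that time and says "Treatment utilization will be categorized by the type of treatment the patient had (surgery vs. radiation vs. active surveillance". It gives no look-back period. Section 11.1 agrees on the single time-point: "follow-up assessments will occur at 12 months following the intervention".

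Section 12.4.1 lists as a secondary endpoint "utilization, which will be categorized by the type of treatment the patient received, as determined by chart review at 12 months post-diagnosis". It then notes that some men may have a repeat biopsy "before these secondary endpoints are measured (at 12 months after first consultation", and says that the modeling will take into account "whether or not a patient receives a follow-up biopsy before 12 months (and the timing of this biopsy".

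On data forms, Section 6.1 says only that "A Schedule of Forms is available on the Alliance study webpage, within the Case Report Forms section". Neither that schedule nor the follow-up form named in Section 8.3.2 is reproduced.

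**The concern.** A window that opens at month 6 makes sense if an earlier review has covered months 0 to 6. None is described. Section 3.2.4 requires the consultation to be the first after diagnosis, so those months directly follow the decision that the aids are meant to influence. A site that keeps to the footnote could fail to record surgery or radiation given early, or could class a treated man as being on surveillance. An early repeat biopsy could be absent from the planned modeling.

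Treatment utilization appears in secondary objectives 2.2.1 to 2.2.3, and Section 12.4.2 compares it with a generalized linear mixed model. The biopsy information enters the models for the 12-month endpoints. The primary endpoint, knowledge, is measured straight after the consultation and is not touched.

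**Working it through.** The plan gives no figure to reproduce here. The check is a comparison of windows, followed by an illustration of what missed treatment would do.

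**Windows side by side**

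- Footnote 1: months 6 to 12, which is 6 of the 12 months after the consultation.
- Section 12.4.1, biopsy: any time before 12 months, with timing. Months 0 to 6 are included, so this is an explicit mismatch. The section names no data source for biopsy.
- Section 12.4.1, utilization: type of treatment received, taken from the chart review. It fixes when the review is done, not how far back it reaches. The conflict is by implication.
- Section 8.3.2: the treatment the man had, with no look-back. Again by implication.

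**Other possible sources in the documents**

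- A 6-month visit, call or review: none in Sections 5.0, 8.3 to 8.3.2 or 11.1.
- Baseline booklet (Appendix I): asks which treatment the man prefers, not which he received.
- 12-month booklet (Appendix II): EPIC-26 and the regret scale. Neither records treatment type or biopsy.

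**Illustration**

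These inputs are assumptions, not figures from the documents:

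- true surveillance share (AS) of 0.60 in one group and 0.40 in the other;
- outcome reduced to surveillance versus active treatment;
- logit link (Section 12.4.2 states none) and no allowance for the random site effect;
- a share m of active treatment missed, equal in all arms.

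True odds ratio: (0.60/0.40) / (0.40/0.60) = 2.25.

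(a) Missed treatment coded as surveillance: recorded share = 1 − (1 − AS)(1 − m). At m = 0.5 this is 1 − 0.40 × 0.5 = 0.80 against 1 − 0.60 × 0.5 = 0.70, so the odds ratio is (0.80/0.20) / (0.70/0.30) = 1.71.

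(b) Missed treatment coded unknown and excluded, with every surveillance patient documented as such: recorded odds = AS / [(1 − AS)(1 − m)]. The factor (1 − m) cancels between the groups, so the odds ratio stays at 2.25 for any m below 1. The share excluded is (1 − AS) × m. At m = 0.5 that is 0.40 × 0.5 = 20% and 0.60 × 0.5 = 30%.

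| m | (a) recorded shares | (a) odds ratio | (b) odds ratio | (b) excluded |
|---|---|---|---|---|
| 0 | 0.60 vs 0.40 | 2.25 | 2.25 | 0% and 0% |
| 0.25 | 0.70 vs 0.55 | 1.91 | 2.25 | 10% and 15% |
| 0.5 | 0.80 vs 0.70 | 1.71 | 2.25 | 20% and 30% |
| 0.75 | 0.90 vs 0.85 | 1.59 | 2.25 | 30% and 45% |

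**The case against.** The best defence is that Section 8.3.2, the procedural text, already allows a full review: it asks for a retrospective look at the chart with no limit. A site working from it would record whatever treatment the man had. Even a site working from the footnote would often meet earlier surgery or radiation in notes from months 6 to 12. Harm needs the footnote to be followed literally and earlier treatment mentioned in later notes to be ignored. The follow-up form may also ask for dates from the consultation on.

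This stands as a limit on the consequence, but it does not remove the mismatch. The footnote is the only text that sets a window, and Section 8.3.2 does not override it. With about 20 sites expected, some may follow one text and some the other. Because sites are the randomized units, uneven abstraction would not necessarily balance across arms, a case that the equal-m illustration does not cover.

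A reader might infer that Section 12.4.1 expressly demands treatment data for all 12 months. It does not; only the biopsy clause carries an explicit period. Nor does it say that biopsy data come from the chart review; that is simply the only follow-up chart source visible.

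**Conclusion.** The protocol text is inconsistent and should be reconciled. The mismatch is explicit for follow-up biopsy and implied for treatment utilization. Confidence is high for the text conflict only.

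The size of any effect is unknown and may be zero. A reader might infer that data for months 0 to 6 will be lost, but the documents do not support this, because the form and the Schedule of Forms cannot be seen and later notes may fill the gap. A reader might also infer that arm differences in utilization would shrink in proportion to the treatment missed. That holds for absolute differences in case (a): 20 points become 0.80 − 0.70 = 10 points at m = 0.5. The plan, however, names a generalized linear mixed model. If its link is logit, the odds ratio falls less, to 1.71, and in case (b) it does not fall at all; the cost there is patients and precision. These figures rest wholly on the assumed 60% and 40%, a two-category outcome and equal m in all arms.

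Only secondary endpoints are at stake. Charts persist, so the matter can be put right if the wording is settled before abstraction.

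**What to change.** Change footnote 1 so that the single 12-month review covers the chart from the initial consultation to the 12-month time-point. Have it record the type and start date of each treatment and the date of any follow-up biopsy. State the same window in Section 8.3.2 and in the follow-up form instruction.

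The cost is one footnote, one phrase and one form instruction. The look-back grows from 6 to 12 months within the same chart review, with no new visit or patient contact.

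A separate clerical point can be settled in the same edit. Section 12.4.1 dates the utilization review from diagnosis, while its own later sentence and Section 8.3 count from the consultation, and the calendar counts from baseline. One anchor should be used throughout.
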